11.6 Investigational Devices Accountability

The Sponsor ships investigational products only to the Principal Investigator (the responsible leader of the investigational site) or his/her authorized designee at each site, after sites meet the requirements of site activation and shipping authorization is complete.

The Investigator or an authorized designee must maintain adequate records of the receipt and disposition of each investigational device, including part number, batch number, and serial number (if applicable), date used, subject identification, and treating physician.

Storage locations for the devices at investigational sites must be locked with access restricted only to Investigators and authorized personnel.

All investigational devices that are associated with a device failure or device deficiency must be returned immediately to the Sponsor.

12.0 ETHICAL CONSIDERATION

12.1 Institutional Review Board Review and Approval

IRB approval for the CIP and ICF/other written information provided to the subject will be obtained by the Principal Investigator at each investigational site prior to consenting and registering subjects in this clinical investigation. The approval letter must be received prior to the start of this clinical investigation and a copy must be provided to the Sponsor.

Any amendments to the CIP as well as associated ICF changes will be submitted to the IRB and written approval obtained prior to implementation, according to each institution's IRB requirements.

No changes will be made to the CIP or ICF or other written information provided to the subject without appropriate approvals, including IRB, the Sponsor, and the regulatory agencies (if applicable).

Until the clinical investigation is completed, the Investigator will advise his/her IRB/EC of the progress of this clinical investigation, per IRB requirements. Written approval must be obtained from the IRB yearly to continue the clinical investigation, or according to each institution's IRB requirements.

No investigative procedures other than those defined in this CIP will be undertaken on the registered subjects without the written agreement of the IRB and the Sponsor.

13.0 CLINICAL INVESTIGATION CONCLUSION

The clinical investigation will reach its end when the last subject registered completes the 90-day follow-up visit. The Sponsor will submit the clinical investigation report within 6 months of the end of the investigation.

The clinical investigation will be concluded when:

- All sites are closed AND

- The final report has been provided to investigators or the Sponsor has provided formal documentation of clinical investigation closure.

14.0 PUBLICATION POLICY

The data and results from the clinical investigation are the sole property of the Sponsor. The Sponsor shall have the right to access and use all data and results generated during the clinical investigation. The Investigators will not use this clinical investigation-related data without the written consent of the Sponsor for any purpose other than for clinical investigation completion or for generation of publication materials, as referenced in the Clinical Trial Agreement. Single-center results are not allowed to be published or presented before the multi-center results. Any proposals for publications or presentations by the investigators must be reviewed and approved by the Sponsor in a timely manner to enable Sponsor review in compliance with the Sponsor's publication policy set forth in the Clinical Trial Agreement.

The Sponsor will register the clinical trial on www.clinicaltrials.gov, in accordance with the International Committee of Medical Journal Editors guidelines, or any other applicable guidelines. The Sponsor shall be responsible for any such registration and results posting as required by ClinicalTrials.gov. Investigational sites shall not take any action to register the trial. A full report of the pre-specified outcomes, including any negative outcomes, will be made public through the ClinicalTrials.gov website according to the requirements of Section 801 of the FDA Amendments Act. If this clinical investigation is terminated early, the Sponsor will make every effort to hasten the release of the pre-specified outcomes through ClinicalTrials.gov website.

15.0 RISK ANALYSIS

15.1 Anticipated Clinical Benefits

The HeartMate PHP may provide hemodynamic support during high-risk PCI by increasing output from the left ventricle to the ascending aorta at a flow rate of over 4.0 L/min against a differential pressure of 60 mmHg. The potential benefits of hemodynamic support using the HeartMate PHP include, but may not be limited to, the following:

- Reduced or eliminated periods of coronary ischemia
- More complete revascularization than would be possible without HeartMate PHP support, and
- Reduction or elimination of intraprocedural complications such as hypotension.

15.2 Anticipated Potential Adverse Events

Risks associated with the HeartMate PHP and procedure, together with their likely incidence, are described in **Appendix IV**.

Anticipated potential adverse events associated with use of the HeartMate PHP are listed below:

- Aortic Insufficiency
- Aortic Valve Injury
- Bleeding
- Cardiac Arrhythmias
- Cardiogenic Shock
- Cardiac Tamponade
- Cerebrovascular Accident
- Death
- Device Malfunction
- Emergent Surgery
- Endocarditis
- Hemolysis
- Hepatic Dysfunction
- Hypertension
- Hypotension
- Insertion Site Infection
- Left Ventricular Perforation
- Limb Ischemia
- Myocardial Infarction
- Myocardial Ischemia
- Renal Dysfunction or Failure
- Respiratory Dysfunction
- Sepsis
- Thrombocytopenia
- Thromboembolism
- Transient Ischemic Attack
- Vascular Access Site and Access-related Complications and Vascular Injury

Anticipated potential adverse events associated with other procedures in this investigation beyond what is anticipated in high-risk PCI:

- Pulmonary Vasculature Injury (see **Section 15.4**)

There may be risks related to the device that are unknown at present. Likewise, the exact frequency of the risk may be unknown.

15.3 Residual Risks Associated with the Device Under Investigation

The HeartMate PHP Risk Management Report* utilizes the Failure Modes and Effects Analysis (FMEA) tool to systematically identify potential hazards associated with the process, design, components, and use of the HeartMate PHP System. Based upon preclinical, clinical and bench data, all residual risks are appropriate and acceptable. The benefit of treatment from the HeartMate PHP outweighs the potential risks to the patient.

As of January 2017, the HeartMate PHP has been used in more than 290 patients clinically and commercially. Comprehensive analysis of clinical data confirms that any undesirable risks identified are outweighed by the potential clinical benefits of the device²⁷.

Residual risks are likewise disclosed in the IFU in the form of clear instructions of what actions to take or to avoid, to avoid a hazardous situation of harm from occurring (contraindications, warnings, and precautions). The anticipated AEs disclosed in the IFU (and CIP Appendix IV) provide further information to enable the user, and potentially the patient, to make an informed decision that weighs the residual risk against the benefit of using the device.

*RISKD, Risk Management Report, HeartMate PHP (High-Risk PCI Indication) # 1012172

15.4 Risks Associated with Participation in this Clinical Investigation

The potential risks associated with HeartMate PHP use are included in **Section 15.2** and **Appendix IV**. The risks are in general consistent with those in procedures such as diagnostic cardiac angiography and PCI. As the HeartMate PHP will be inserted into the left ventricle through the aortic valve, there might be potential risks of aortic valve injury or insufficiency associated with the use. However, the risks of valve injury or insufficiency also exist in cardiac angiography and/or PCI procedures²⁹⁻³⁴, albeit at a much lower rate compared to the risk of such during participation in this clinical investigation. The exact rate of valve injury or insufficiency resulting from angiography or PCI is not presently known.

[REDACTED]

[REDACTED]

[REDACTED]

15.5 Steps That will be Taken to Control or Mitigate Risks

In-depth recommendations, special precautions and instructions regarding subject selection, device handling, physician training, device placement and system removal are included in the IFU/IB. Mitigations and treatment for all adverse events will be performed per the current practice standards/standards of care as determined by the Investigator.

Risks associated with the use of the HeartMate PHP during this clinical investigation are minimized through device design, investigator selection and training, pre-specified subject eligibility requirements, study monitoring to ensure adherence to the CIP, and the use of a DSMB. Furthermore, the Sponsor will provide a trained product field specialist for every HeartMate PHP system used in the clinical investigation.

These risk management aspects are detailed below:

Device Design

[figure not shown]
Investigator Selection and Training:

It is also stated in the IFU that the devices can only be used by physicians who have received appropriate training on how to use the device. This statement is interpreted to mean that the physician users must complete Sponsor-provided device training prior to clinical use and are expected to be aware of the known and foreseeable safety risks associated with the use of the devices including the surgical and/or non-surgical treatment of these conditions.

- Only physicians who are skilled in the manipulation of catheter-based technology in the vasculature and heart, and have a good understanding of the risks associated with these manipulations, will be selected as investigators for this clinical investigation.
- Site investigators will undergo training on the techniques required to optimally place and operate the device in the left ventricle. The physician users are expected to be aware of the known and foreseeable safety risks associated with the use of the devices, including the surgical and/or non-surgical treatment of these conditions.
- Emergency surgical back-up should be available as per the institution's standard procedures.
- Each case would be supported by Abbott field personnel.
- Pre-specified patient eligibility requirements - as stated in **Section 5.3** of the CIP.

Ensuring Strict Adherence to the CIP

The clinical investigation will be carefully monitored by the Sponsor monitor (or designee) to ensure adherence to the CIP. Adverse events and device deficiencies will be reported to the Sponsor/designee and will be monitored internally for safety surveillance purposes. A DSMB will be used for the clinical investigation. Stopping rules will be discussed with the DSMB and applied for subject safety through enrollment.

15.6 Risk to Benefit Rationale

Patients with complex coronary anatomy or depressed left ventricular function undergoing PCI may be at risk of hemodynamic collapse during PCI due to decreases in coronary perfusion during balloon inflations or in the event of complications such as vessel occlusion or dissection. These patients undergoing high-risk PCI may require the use of hemodynamic support devices. The HeartMate PHP is a high-flow, rapid-insertion percutaneous left ventricular assist devices which can provide hemodynamic support during high-risk PCI by increasing output from the left ventricle to the ascending aorta at a rate of over 4.0 liters per minute, which may provide hemodynamic stabilization for the patient. The potential benefits of hemodynamic support using the HeartMate PHP include reduced or eliminated periods of coronary ischemia, more complete revascularization than would be possible without HeartMate PHP support, and reduction or elimination of intraprocedural complications such as hypotension.

[figure not shown]
While there may be potential risks associated with the use of HeartMate PHP as listed in **Section 15.2 and Appendix IV**, these risks are in general consistent with those in procedures such as diagnostic cardiac angiography and PCI. Hemodynamic collapse may lead to severe consequences including death. Given the potential reduction in the risk of hemodynamic collapse during high-risk PCI that the HeartMate System can provide, the potential benefits outweigh the potential risks associated with the use of the HeartMate PHP System.

[figure not shown]
APPENDIX I: ABBREVIATIONS AND ACRONYMS

Acronym or Abbreviation	Complete Phrase or Definition
AE	Adverse event
ACT	Activated clotting time
ALT	Alanine aminotransferase
AMI	Acute myocardial infarction
APTT	Activated partial thromboplastin time
AST	Aspartate aminotransferase
AT	As-treated
BARC	Bleeding Academic Research Consortium
BUN	Blood urea nitrogen
CABG	Coronary artery bypass graft
CAD	Coronary artery disease
CCS	Canadian Cardiovascular Society
CE	Conformité Européene
CEC	Clinical Events Committee
CFR	Code of Federal Regulations
CI	Cardiac index
CO	Cardiac output
CPO	Cardiac power output
CPR	Cardiopulmonary resuscitation
FDA	Food and Drug Administration
CK	Creatine kinase
CK-MB	Creatine kinase myocardial-band isoenzyme
CRF	Case report form
CTA	Clinical trial agreement
CVA	Cerebrovascular accident (or stroke)
dL	Deciliter
DSMB	Data Safety Monitoring Board
DMP	Data Management Plan
ECG	Electrocardiogram
eCRF	Electronic case report form
EDC	Electronic data capture

Acronym or Abbreviation	Complete Phrase or Definition
FDA	Food and Drug Administration (U.S.)
FFR	Fractional flow reserve
FMEA	Failure modes and effects analysis
GCP	Good clinical practice
HIPAA	Health Insurance Portability and Accountability Act
IABP	Intra-aortic balloon pump
IB	Investigator Brochure
ICF	Informed Consent Form
ICU	Intensive care unit
IDE	Investigational Device Exemption
IFU	Instructions for Use
INR	International normalized ratio
IRB	Institution Review Board
ITT	Intent-to-treat
IVRS	Intravascular ultrasound
LDH	Lactate dehydrogenase
LVEF	Left ventricular ejection fraction
MAP	Mean arterial pressure
MHRA	Medicines and Healthcare Products Regulatory Agency
MI	Myocardial infarction
mm	Millimeter
NYHA	New York Heart Association
OUS	Outside the United States
PfHgb	Plasma-free hemoglobin
PAP	Pulmonary arterial pressure
PCI	Percutaneous coronary intervention
PCWP	Pulmonary capillary wedge pressure
PP	Per-protocol
PTT	Partial thromboplastin time
RAP	Right atrial pressure
SAE	Serious adverse event

Acronym or Abbreviation	Complete Phrase or Definition
SAP	Statistical Analysis Plan
SAQ	Seattle Angina Questionnaire
SBP	Systolic blood pressure
STEMI	ST elevation myocardial infarction
STS	Society of Thoracic Surgery
TIA	Transient ischemic attack
UADE	Unanticipated adverse device effect
ULN	Upper limit of normal
US	United States
USADE	Unanticipated serious adverse device effect

[figure not shown]

[figure not shown]

[figure not shown]

[figure not shown]
Study Document Number: [REDACTED]

[figure not shown]
Study Name: SHIELD II

[figure not shown]

[figure not shown]

[figure not shown]

Study Document Number: [REDACTED]
Study Name: SHIELD II

Study Document Number: [REDACTED]
Study Name: SHIELD II

[REDACTED]
[REDACTED]

[REDACTED]
[REDACTED]

Study Document Number: [REDACTED]

Study Name: SHIELD II

[REDACTED]

[REDACTED]

[REDACTED]

[REDACTED]

[REDACTED]

Study Document Number: [REDACTED]

Study Name: SHIELD II

[REDACTED]

[REDACTED]

[REDACTED]

[REDACTED]

[figure not shown]
[REDACTED]

[figure not shown]
[REDACTED]

[figure not shown]
[REDACTED]

[figure not shown]
[REDACTED]

[figure not shown]
[REDACTED]

[figure not shown]

[figure not shown]

Abbott

Study Document Number:

Study Name: SHIELD II

1.0 SYNOPSIS OF STUDY DESIGN

1.1 Purpose of the Statistical Analysis Plan

This statistical analysis plan (SAP) is to provide a detailed and comprehensive description of the planned methodology and analysis to be used for Clinical Investigation Plan (CIP) 10148, the SHIELD II clinical investigation. This plan is based on the Version J Clinical Investigation Plan.

1.2 Clinical Investigation Objectives

The objective of the SHIELD II clinical investigation is to assess the safety and effectiveness of the HeartMate PHP compared to Impella in supporting patients with severe symptomatic coronary artery disease but with stable cardiovascular function, who are undergoing elective or urgent high-risk PCI, and a heart team, including a cardiac surgeon, has determined high-risk PCI is an acceptable therapeutic option.

1.3 Clinical Investigation Design

SHIELD II is a prospective, randomized, open-label, multi-center clinical investigation that will register subjects at up to 120 sites in the U.S. Subjects in this clinical investigation will be randomly assigned to the HeartMate PHP or Impella in a 2:1 ratio. The primary endpoint is a composite endpoint at 90 days, including cardiovascular death, myocardial infarction (MI), stroke, unplanned repeat revascularization, bleeding of BARC 3 or 5 up to 14 days post-device removal, severe hypotension and change in aortic insufficiency from baseline to 90 days by echocardiographic assessment. HeartMate PHP will be tested for non-inferiority in the primary endpoint compared to Impella. Any Impella device approved for use in high-risk PCI can be used as the control device. All registered subjects will be followed for 90 days. This clinical investigation is conducted to support the pre-market approval of the HeartMate PHP for the indication of high-risk PCI.

The SHIELD II clinical investigation is divided into two phases chronologically: a feasibility phase, which includes subjects registered under the CIP versions 2-4[†] prior to January 30, 2017, and a pivotal phase, which includes subjects to be registered under version F or a later version of the CIP. Both phases consist of a non-randomized roll-in cohort and a randomized cohort. The roll-in cohort is designed to prevent a learning curve from biasing the clinical investigation results.

There were 195 subjects, including 75 HeartMate PHP roll-in and 120 randomized subjects, registered at 48 U.S. sites in SHIELD II prior to January 30, 2017, and these subjects are now considered in the feasibility phase of the clinical investigation. All registered subjects in the

[†] Previous versions of the SHIELD II CIP in the feasibility phase were designated numerically from version 1 to version 5 (no subjects were registered under versions 1 and 5 of the CIP). Starting from the pivotal phase, the CIP is designated alphabetically and starts as version F.

Statistical Analysis Plan

feasibility phase were already beyond the time point of the 90-day follow-up visit, and the feasibility phase of the clinical investigation reached its end in 2017.

In the pivotal phase, each operator will be required to actively participate in treating a minimum of 1 and up to 2 HeartMate PHP subjects first before becoming qualified to randomize subjects. Since only sites experienced in the use of Impella will be invited to participate in this clinical investigation, no roll-in subjects using Impella will be required in the pivotal phase. With an estimation of 2 operators per site, up to 480 HeartMate PHP roll-in subjects will be registered at up to 120 sites in the U.S. in the roll-in cohort. For the randomized cohort of the pivotal phase, a minimum of 473 subjects will be randomized.

Each site will be allowed a maximum of 60 randomized subjects. The overall design of the SHIELD II clinical investigation is shown in **Figure 1**.

[figure not shown]
Both roll-in and randomized subjects will follow all the clinical investigation procedures outlined in the CIP. The results of the roll-in cohort will be analyzed as adjunctive data, separate from the results of the randomized cohort. In addition, data in the feasibility phase of the clinical investigation will also be analyzed separately from data in the pivotal phase of the clinical investigation. Hypothesis testing of the primary endpoint will be performed for the randomized cohort in the pivotal phase to support regulatory approval.

The clinical investigation has been designed to involve as little pain, discomfort, fear, and any other foreseeable risk as possible for subjects. Refer to the Risk Analysis section of this clinical investigation plan for details.

Statistical Analysis Plan

Figure 1: Overall Design of the SHIELD II Clinical Investigation

The SHIELD II trial Pivotal Phase will not enroll patients in Europe.

* The feasibility phase of the clinical investigation has already completed the 90-day follow-up and reached its end as of the release of Revision F of this CIP.

Statistical Analysis Plan

1.4 Endpoints

The primary endpoint analysis will be based on adverse events collected after the start of the index procedure.

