6.3 Index Procedure

6.3.1 Right Heart Catheterization

Right heart catheterization is required to obtain hemodynamic measurements, and the placement of the catheter for the right heart catheterization will need to be done before inserting the study device and performing the PCI procedure for revascularization. In this CIP, the beginning of the index procedure is defined as the insertion of the first vascular access during the index procedure, and the end of the index procedure is defined as the removal of the last vascular access during the index procedure or the exit from the catheterization laboratory, whichever occurs first. In addition, the beginning of the PCI procedure is defined as the insertion of the first guiding catheter for the lesion(s) to be revascularized during this index procedure, and the end of the PCI procedure is defined as the removal of the last guiding catheter for the lesion(s) to be revascularized during this index procedure.

Hemodynamic Assessments

Hemodynamic assessments will be performed at the following four time points:

- 1) Prior to device insertion
- 2) Prior to the PCI procedure while on device support
- 3) Immediately prior to weaning for the preparation of device shutdown and removal
- 4) 10 to 30 minutes after device removal

The following hemodynamic measurements at each of the time points above and the corresponding study pump parameters at time points 2) and 3) above need to be collected and recorded:

- Right atrial pressure (RAP)
- Pulmonary artery pressure (PAP)
- Pulmonary capillary wedge pressure (PCWP)
- Cardiac output (CO)*
- Cardiac index (CI)*
- Cardiac power output (CPO)
- Mean arterial pressure (MAP)
- Heart rate
- Corresponding pump speed of PHP or Impella at time points 2) and 3)

- Corresponding estimated pump flow of PHP or Impella at time points 2) and 3)

***Note:** The Fick method is required to measure CO and CI. A second method using thermodilution can be optional.

Hemolysis Biomarker Assessment

Hemolysis biomarkers include plasma free hemoglobin and lactate dehydrogenase (LDH). Two blood draws during the index procedure are required for the assessment.

1. Pre-device draw: Blood will be collected before device insertion via a vascular access sheath (could be venous or arterial, and with no other catheter/device simultaneously inserted in the sheath) in the catheterization laboratory during the index procedure for the assessment of both plasma free hemoglobin* and LDH.

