7.3 Adverse Event and Device Deficiency Reporting

7.3.1 Adverse Event Reporting

Safety surveillance and reporting starts as soon as the subject is registered in the clinical investigation. Safety surveillance and reporting will continue until the last follow-up visit has been performed, the subject is deceased, the subject concludes participation in the clinical investigation or the subject withdraws from the clinical investigation. All adverse event data, including deaths and device deficiencies, will be collected throughout the time period defined above and will be reported to the Sponsor on a CRF. Additional information with regard to an adverse event should be updated within the appropriate CRF.

Unchanged, chronic, non-worsening or pre-existing conditions are not AEs and should not be reported.

An offline form will be made available to allow the investigator to report SAEs in the event the entry cannot be made in the EDC. This does not replace the EDC reporting system. All information must still be entered in the EDC system as soon as feasible.

Non-cardiac related abnormal laboratory values will not be considered AEs unless:

1. The investigator determined that the value is clinically significant,
2. The abnormal lab value required intervention, or
3. The abnormal lab value required subject withdrawal from the clinical investigation.

In this clinical investigation, all adverse events, regardless of their relationship to the devices, are to be documented on the appropriate CRF throughout the 90-day follow-up visit. Anticipated adverse event definitions can be found in **Appendix II**.

SAE Reporting

The investigator should report all SAEs to the Sponsor as soon as possible but no later than the timelines outlined below.

Clinical Site	Reporting timelines
All Sites	SAEs must be reported to the Sponsor no later than 3 calendar days from the day the site personnel became aware of the event or as per the investigative site's local requirements, if the requirement is more stringent than those outlined above.

The date the site staff became aware the event met the criteria of an SAE must be recorded in the source document. The Investigator will further report the SAE to the local IRB according to the institution's IRB reporting requirements.

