1.5.2 Timing of Randomization

Randomization assignments will be given through EDC Study Site Portal after subjects have signed the ICF and met all eligibility requirements. Subjects will be considered registered in the clinical investigation once randomized and must follow all CIP requirements. Randomized subjects who do not undergo device placement due to previously undiagnosed anatomic abnormalities (e.g. peripheral vascular disease) which precludes device placement, will be considered registered and in the intent-to-treat (ITT) population, and they must follow all CIP requirements. Once a subject is randomized, PCI should be performed as soon as possible.

[REDACTED]

[REDACTED]

Statistical Analysis Plan

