1.6 Blinding

This is an open-label clinical investigation. The subjects and the investigators will not be blinded to the treatment assignment. Nevertheless, measures of blinding will be taken to minimize bias and will be applied to the randomized cohorts of both the feasibility and pivotal phases.

[figure not shown]

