2.2.2 Descriptive Statistics for Categorical Variables

For binary variables (e.g. gender, diabetic status, etc.), results within treatment arm will be summarized with subject counts and percentages/rates, and where applicable, with exact 95% Clopper-Pearson¹ confidence intervals.

For events of interest, relative risks (i.e., the ratio of rates), confidence interval for the relative risks, the difference in rates and the confidence interval for difference in rates, and p-values may also be presented for hypothesis generating purposes.

For the determination of event rates, the denominators are defined as below based on the type of events.

- Primary endpoint event and its components

The denominator of the primary endpoint event rate will exclude subjects in the analysis population who terminated from the study [REDACTED] without a primary endpoint event or any subject who completes the 90-day follow-up without aortic insufficiency data at either baseline or 90-day follow-up and without a primary endpoint event. The same denominator rule will apply to individual component of the primary endpoint except for change in aortic insufficiency, which is an imaging endpoint and will follow the denominator rule set forth for missing data handling.

Statistical Analysis Plan

- Site-reported Adverse Events, Adverse Device Effects and Adverse Event related Descriptive Endpoints

[REDACTED]

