2.3 Endpoint Analysis

2.3.1 Primary Endpoint(s)

The primary endpoint, a composite of safety and effectiveness at 90 days, will be evaluated using the difference in event rates in the ITT population of the pivotal phase. The hypothesis test is designed to show non-inferiority of HeartMate PHP to Impella for the primary endpoint with one-sided alpha of 0.025.

[REDACTED]

ICER

[REDACTED]

If non-inferiority is met, superiority testing will be performed with a two-sided alpha of 0.05.

[REDACTED]

[REDACTED]

The data will be analyzed for superiority using Fisher's exact test.

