3.3 Subject Early Termination

Subject early termination reasons including deaths, withdrawals, lost-to-follow-up, etc. will be summarized by treatment arms at the 90-day follow-up visit.

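### SAP 1.4 leaves events between open-label randomization and first vascular access out of the ITT primary count, and no named sensitivity analysis visibly restores the non-fatal ones

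*SAP*

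**What the plan says.** **Population and assignment.** Under SAP 2.3.1 the primary endpoint "will be evaluated using the difference in event rates in the ITT population of the pivotal phase". SAP 1.5.2 fixes entry at randomization: "Subjects will be considered registered in the clinical investigation once randomized". The same section keeps in the ITT population randomized subjects whose previously undiagnosed anatomy prevents device placement. Assignment is open: "The subjects and the investigators will not be blinded to the treatment assignment" (SAP 1.6).

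**Collection.** Protocol 7.3.1: "Safety surveillance and reporting starts as soon as the subject is registered in the clinical investigation". Deaths are expressly included. Table 2 in Protocol 6.9 first marks adverse event assessment in the intraprocedure column, but 7.3.1 is explicit about the earlier start.

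**Counting.** SAP 1.4: "The primary endpoint analysis will be based on adverse events collected after the start of the index procedure". Protocol 6.3.1 supplies the date: "the beginning of the index procedure is defined as the insertion of the first vascular access during the index procedure". The endpoint definition in Protocol 4.1 carries no such restriction.

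**Denominator and other reporting.** SAP 2.2.2: "The denominator of the primary endpoint event rate will exclude subjects in the analysis population who terminated from the study", for those without a primary endpoint event and subject to a redacted clause. SAP 3.3: "Subject early termination reasons including deaths, withdrawals, lost-to-follow-up, etc. will be summarized by treatment arms at the 90-day follow-up visit". SAP 3.2 takes the start of the index procedure as the reference time for adverse event summaries, and summarizes adjudicated events by arm for all registered subjects.

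**The concern.** An ITT comparison normally counts outcomes from the moment of assignment. Here collection starts at randomization and counting starts at first vascular access, so events in between drop out of the primary test. Both the investigator and the subject know the arm during that interval, so a difference between arms in delay or cancellation cannot be excluded by design. A subject who never reaches vascular access stays in the ITT population but has no visible start to the counting window.

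The stake is the non-inferiority conclusion, which rests on a 10-point margin and a few hundred subjects. Close to the margin, one event more or less can decide it.

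**Working it through.** **Which components are affected.** Cardiovascular death, MI, stroke and BARC 3/5 bleeding can all occur before access. An unplanned revascularization can too, if the redacted definitions would call it a repeat procedure. Severe hypotension is defined on device support and change in aortic insufficiency is an imaging comparison, so neither is affected.

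**What happens to a subject with a pre-access event.**
- *Non-fatal, follow-up completed, aortic insufficiency data present:* the subject stays in the denominator as a non-event. Nothing is missing. Worst-case, tipping-point and multiple-imputation analyses (SAP 2.12, details redacted) by their names address missing outcomes, so none visibly restores this event.
- *Fatal:* SAP 3.3 treats death as an early termination. Depending on the redacted clause in SAP 2.2.2, the subject may leave the denominator. The outcome would then be missing and the same sensitivity analyses may cover it. The death would also appear by arm under SAP 3.3.

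**Inputs.** Impella rate 20%, margin 10 points, 315 and 158 subjects (SAP 2.4); one-sided alpha 0.025 (SAP 2.3.1); maximum 716 subjects, split 477 and 239 (assumed from 2:1). The documents give no pre-access event count, so every loss below is an assumption. The non-inferiority test itself is redacted, so an unpooled test is assumed. The sample size of 473 is not in dispute. It cannot be uniquely reproduced, because the assumed PHP rate, the power and the attrition are not visible.

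**Formula.** At the non-inferiority boundary the true rates are 30% (PHP) and 20% (Impella). With counted rates pT and pC,

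type I error = Φ[(0.10 − (pT − pC))/SE − 1.960], where SE = √[pT(1 − pT)/nT + pC(1 − pC)/nC].

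**Plan's own figure first.** With no loss, the numerator is 0 and the result is Φ(−1.960) = 2.50%, the nominal level.

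**One net PHP event uncounted, n = 473.** pT = 0.30 − 1/315 = 0.29683; SE = 0.0409; (0.10 − 0.09683)/0.0409 = 0.078; Φ(−1.882) = 2.99%.

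**One net Impella event uncounted, n = 473.** pC = 0.20 − 1/158 = 0.19367; the difference is 0.10633; SE = 0.0407; −0.00633/0.0407 = −0.156; Φ(−2.116) = 1.72%.

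| Assumed loss | n = 473 | n = 716 |
|---|---|---|
| None | 2.50% | 2.50% |
| Same absolute rate in both arms (e.g. 2 PHP and 1 Impella) | 2.50% | 2.50% |
| One net PHP event scored as a non-event | 2.99% | 2.89% |
| One PHP subject leaves the denominator, pT = (0.30nT − 1)/(nT − 1) | 2.84% | 2.77% |
| One net Impella event scored as a non-event | 1.72% | 1.85% |

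**Exact check.** Binomial enumeration of the assumed unpooled test gives 2.22% (n = 473) and 2.25% (n = 716) with no loss. With one net PHP event uncounted it gives 2.67% and 2.61%. The rise is 0.45 and 0.36 points, against 0.49 and 0.39 in the normal approximation.

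**One event at the margin (illustrative counts).** Impella 32/158 = 20.25%.
- PHP 70/315 = 22.22%: difference 1.97 points, SE 3.96, Wald upper 97.5% bound 1.97 + 1.96 × 3.96 ≈ 9.74. Non-inferiority is met.
- PHP 71/315 = 22.54%: difference 2.29 points, SE 3.97, bound 2.29 + 1.96 × 3.97 ≈ 10.07. It is not met.

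**The case against.** The case for leaving the plan alone is respectable.

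- **The interval is probably short.** PCI is to follow randomization promptly (SAP 1.5.2). Some exclusions look back 24 hours from the procedure (Protocol 5.3.2.1), and baseline cardiac biomarkers are due within 48 hours before it (Protocol 6.1). This stands. No maximum interval is visible, though redacted text in the timing section could contain one.
- **No study device has been used before access.** The natural expectation is the same pre-access event rate in both arms, and that leaves the type I error unchanged. This also stands.
- **A procedure-based window is coherent** for a comparison of peri-procedural support devices, and it is prespecified and symmetric. That makes replacing the primary window debatable. It does not explain why an ITT analysis should have no from-randomization count at all.
- **Other tables may show these events.** Deaths should be visible under SAP 3.3. For non-fatal events it is unclear whether procedure start in SAP 3.2 is a day zero or a filter. Neither table enters the primary test.

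A reader might infer that the rule tilts the trial toward non-inferiority. The documents do not support that: they show no mechanism for an excess of pre-access events in the PHP arm, and an excess in the Impella arm works the other way. A reader might also infer that pre-access deaths vanish from the analysis. That depends on redacted wording in SAP 2.2.2, and the missing-outcome analyses may pick them up.

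**Conclusion.** The gap is real on unredacted text: post-assignment events are reported but not counted in an ITT primary analysis. The clear remainder is the non-fatal pre-access event in a subject with complete follow-up, who is scored event-free with no visible analysis to show the difference.

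The size is unknown and probably small, and the direction is unknown. Equal rates in both arms cost nothing. One net uncounted PHP event adds about 0.4 to 0.5 points to the type I error, and one net uncounted Impella event makes the test conservative. These figures assume an unpooled test, true rates of 30% and 20%, and loss counts the documents do not give. The point justifies an inexpensive safeguard for a result that one event can flip. It does not show that the planned primary analysis is invalid.

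**What to change.** Before unblinding, amend the SAP in two places.

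1. Prespecify an ITT sensitivity analysis of the primary endpoint that counts cardiovascular death, MI, stroke, unplanned revascularization and BARC 3/5 bleeding from randomization. Preferably make this the ITT count, and keep the procedure-start window for the as-treated and per-protocol analyses.
2. Report by arm the number of subjects with no index procedure and the number with events between randomization and first vascular access.

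The cost is SAP wording and one table, because Protocol 7.3.1 already requires the events to be reported from registration. The downside is a few added events unrelated to the device, in both arms.
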